Study Objectives	
Primary
 
 
1. To assess the safety and tolerability of lung SBRT in combination with pembrolizumab.
 
2. To determine the recommended dose of lung SBRT to be used in combination with pembrolizumab in a phase 2 trial.
 
 
Secondary
 
 
1. To describe the safety profile of lung SBRT in combination with pembrolizumab.
 
2. To assess clinical benefit by calculating the overall responses rates (ORR) and disease control rate (DCR).
 
3. To assess responses rates in squamous versus non-squamous histological subtypes of NSCLC.
 
4. To assess response rates in relation to tumour PD-1/PD-L1 expression.
 
5. To assess progression free survival (PFS) and overall survival (OS).
 
 
Exploratory

	
 
To identify biomarkers that correlate with immunological response to therapy.
 
To analyse peripheral blood samples for ctDNA.
 

Study Endpoints	
Primary
 
 
To establish the maximum tolerated dose (MTD) and recommended dose for phase 2 trials (RP2D) of lung SBRT that can be safely combined with pembrolizumab.
 
 
Secondary
 
 
To assess the rates of acute toxicity (defined as up to 12 weeks after the last fraction of lung SBRT) using CTC AE v4.0.
 
To assess the rates of late toxicity (defined as from 12 weeks after last fraction of lung SBRT until 28 days after the last dose of pembrolizumab) using CTC AE v4.0.
 
To calculate the ORR and DCR using RECIST v1.1 & irRC.
 
To calculate the ORR and DCR in a squamous versus non-squamous histological subtype using RECIST v1.1 & irRC.
 
To assess the frequency of PD-1/PD-L1 expression distribution in responders and non-responders.
 
To measure the PFS and OS at 6 and 12 months.
 
 
Exploratory
 
 
To characterize tumour infiltrating lymphocytes and tumour antigens in the tumour biopsies. These immunohistochemistry analyses will include, but not necessarily be limited to, the following markers: CD4, CD8, FOXP3, PD-1, PD-L1, and PD-L2.
 
To assess for levels of ctDNA before and after lung SBRT
 

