#### **2.1.2 Secondary Objectives**

- To describe the safety profile of lung SBRT in combination with pembrolizumab.
- To assess clinical benefit with overall responses rate (ORR) and disease control rate (DCR).
- To assess responses rates in squamous versus non-squamous histological subtypes of NSCLC.
- To assess response rates in relation to tumour PD-1/PD-L1 expression.
- To assess progression free survival (PFS) and overall survival (OS).

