### **2.2.2 Secondary Endpoints**

- To assess the rates of acute toxicity (defined as up to 12 weeks after the last fraction of stereotactic radiotherapy) using CTC AE v4.0.
- To assess the rates of late toxicity (defined as from 12 weeks after last fraction of lung SBRT until 28 days after the last dose of pembrolizumab) using CTCAE version 4.0.
- To calculate the ORR and DCR using RECIST v1.1 & irRC.
- To calculate the ORR and DCR in squamous versus non-squamous histological subtype using RECIST v1.1 & irRC.
- To assess the frequency of PD-1/PD-L1 expression distribution in responders and non-responders.
- To measure the PFS and OS at 6 and 12 months.

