#### 8.1.2 Secondary Endpoints

Acute and late toxicity data will be tabulated by type, grade and dose level with the number, proportions and frequencies of grades 1-4 and grade 3-4 grades reported. The duration of clinical benefit assessed by overall response rate (ORR) defined as complete response (CR) or partial response (PR) and disease control rate (DCR) defined as CR, PR or stable disease (SD) using RECIST v1.1 & irRC (Appendix 6 & 7) will be calculated as a proportion of total treated with a 95% confidence interval. Differential response rates, defined as mixed responses , where some sites of disease shows a response to treatment, while other sites of disease show disease progression, will be measured as (yes/no). This will be calculated as proportions in the squamous cell and non-squamous cell histological sub-type giving associated 95% confidence intervals. Any differences will be assessed using a Chi squared test for proportions on differential response rates between histological subtypes. **PD-L1 staining is referred to as tumour proportionate score, reported as a percentage**

from 0–100%. It is classed as weakly positive (1 – 49%); strongly positive if >50%; and negative if <1%. The effect of PD-L1 expression on response rates will be measured using the proportion of patients recorded to be weakly positive, strongly positive or negative and tested using a Chi Squared test for proportions on expression level between responders and non-responders. PFS will be measured from the start of radiotherapy until radiological or clinical evidence of progression or death and will be censored at date of last follow-up for surviving patients. OS will be measured from the start of radiotherapy until death and will be censored at date of last follow-up for surviving patients. Median PFS and OS will be calculated using Kaplan-Meier methods giving associated 95% confidence intervals, respectively. All patients from Part A and Part B will be used to analyse secondary endpoints.

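### Section 8.1.2 compares mixed response by histology, while the stated secondary endpoint is ORR and DCR by histology

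*Combined protocol and SAP*

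**What the plan says.** The objective in section 2.1.2 is "To assess responses rates in squamous versus non-squamous histological subtypes of NSCLC". The matching endpoint in section 2.2.2 is "To calculate the ORR and DCR in squamous versus non-squamous histological subtype using RECIST v1.1 & irRC", and the Trial Summary repeats it ("To calculate the ORR and DCR in a squamous versus non-squamous histological subtype").

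The analysis is in section 8.1.2. It defines ORR as CR or PR and DCR as CR, PR or SD, and says these "will be calculated as a proportion of total treated with a 95% confidence interval". It then introduces differential response, defines it as mixed response ("where some sites of disease shows a response to treatment, while other sites of disease show disease progression") and codes it yes/no. The next two sentences cover histology: "This will be calculated as proportions in the squamous cell and non-squamous cell histological sub-type giving associated 95% confidence intervals", then "Any differences will be assessed using a Chi squared test for proportions on differential response rates between histological subtypes". All Part A and Part B patients enter the secondary analyses.

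The same section classes PD-L1 staining as weakly positive at 1–49%, and "strongly positive if >50%; and negative if <1"%.

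**The concern.** Mixed response is a different variable from ORR or DCR, and no objective or endpoint asks for it. A statistician following section 8.1.2 literally would tabulate and test it by histology, and would report ORR and DCR only for the whole cohort. The one p-value on histology would then not concern response rate. The named endpoint would have no analysis sentence of its own, with no subtype denominator, no interval and no comparison. What to report for it would be settled only after the data were seen.

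Mixed response is also not fully defined. Section 8.1.2 gives no threshold for calling a single site responding or progressing, and neither response table (Appendix 6 for RECIST v1.1, Appendix 7 for irRC) has a category for it.

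**Working it through.** **The plan's own number.** Section 8.2 gives two dose levels of 3 to 6 patients, so 6 to 12, plus 12 in expansion. The maximum is 12 + 12 = 24, which agrees with section 3.2. The plan gives no significance level, power or effect size for the histology comparison, so there is nothing further to reproduce.

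**Endpoint against analysis.**

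| | Endpoint (section 2.2.2, Trial Summary) | By-histology analysis (section 8.1.2) |
|---|---|---|
| Variable | ORR and DCR | Mixed response, yes/no |
| Criteria | RECIST v1.1 and irRC | None stated |
| Split | Squamous / non-squamous | Squamous / non-squamous |
| Proportions by subtype | 2 outcomes × 2 criteria × 2 subtypes = 8 | 0 of those 8, plus 2 for mixed response |

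**Whether mixed response can stand in for ORR or DCR.** ORR and DCR classify the patient as a whole, whereas mixed response records opposite behaviour at different sites in one patient. Take a patient whose index lesions shrink while a new lesion appears. In the Appendix 6 table any new lesion makes the overall response PD, so the patient counts against both ORR and DCR. In the Appendix 7 table an index-lesion partial response with any new lesions is irPR, provided total burden including measurable new lesions has fallen by at least 50%. The same mixed responder can therefore be a non-responder under one criterion and a responder under the other. A subtype difference in mixed response thus implies nothing definite about response rates.

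**What the correct analysis could show.** The documents give no rate for mixed response, so the test as written cannot be sized. For ORR, section 1.1.4.2 gives 18.0% in previously treated patients in KEYNOTE-001. The documents give no squamous share; 25% to 50% is assumed here.

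- Expected responders: 24 × 0.180 = 4.32.
- Expected squamous responders: 6 × 0.180 = 1.08 at a 25% share, and 12 × 0.180 = 2.16 at 50%.
- Exact (Clopper–Pearson) 95% CIs for counts near these: 1/6, 0.4% to 64.1%; 3/18, 3.6% to 41.4%; 2/12, 2.1% to 48.4%.

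The difference uses Newcombe's method. With Wilson limits (l, u) for each proportion, the lower limit is d − √[(p₁ − l₁)² + (u₂ − p₂)²] and the upper limit is d + √[(u₁ − p₁)² + (p₂ − l₂)²].

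- 1/6 versus 3/18: the Wilson limits are (0.030, 0.564) and (0.058, 0.392), and d = 0. Lower: −√[(0.167 − 0.030)² + (0.392 − 0.167)²] = −0.264. Upper: √[(0.564 − 0.167)² + (0.167 − 0.058)²] = 0.411. The interval is −26.4 to +41.1 points.
- 2/12 versus 2/12: the Wilson limits are (0.047, 0.448) for both. The half-width is √[(0.167 − 0.047)² + (0.448 − 0.167)²] = 0.306. The interval is −30.6 to +30.6 points.

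The smallest expected cell count is 1.1 to 2.2, so exact intervals suit these data better than a chi-squared test.

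**PD-L1 classes.** The classes below 1%, 1–49% and above 50% leave a score of exactly 50% in none of them. Section 1.1.4.2 itself uses both 50% or more and more than 50% as the high-expression cut-off.

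**The case against.** The strongest reply is that the pieces for ORR and DCR by subtype are present. Section 2.2.2 is phrased as an instruction to calculate them under both criteria. Section 8.1.2 defines them and sets a treated-patient denominator with a 95% CI. Section 8.1 adds frequencies, proportions and exact intervals where appropriate. Nothing says mixed response replaces ORR and DCR by subtype, so both could be reported. The opening word of the by-histology sentence might also refer back to ORR and DCR, or differential response might have been meant as a difference between histologies.

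Part of this stands. A careful statistician could assemble the 8 proportions, and the zero count applies to section 8.1.2 alone. However, the general rules only permit the subtype analysis. They supply no subtype denominator or comparison, and they do not correct an explicit rule written for another variable. The referring word follows directly on the mixed-response sentence, and the test sentence then uses the term just defined. If ORR and DCR were meant, the text still needs correcting.

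It is also fair that the interval widths measure the smallness of the trial and not the defect, that they use the maximum of 24 when 6 + 12 = 18 is possible, and that no DCR figure is computed. They serve only to support descriptive reporting. The PD-L1 point is separate and minor, and the PD-L1 analysis otherwise uses its endpoint's own variable.

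**Conclusion.** The concern holds. The by-histology analysis in section 8.1.2 is attached to a variable that no endpoint lists, and the listed endpoint has no by-histology analysis in that section. This follows from the text and rests on no numerical assumption.

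It should be corrected, but its reach is small: one secondary comparison in at most 24 patients, with no bearing on dose escalation. Under the assumed squamous share and an 18.0% response rate, even the right comparison could not exclude differences of roughly 26 to 41 points in one direction or the other, so it belongs in the report as description without a significance test.

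**What to change.** Replace the by-histology sentences in section 8.1.2 with text to this effect:

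*ORR and DCR, each by RECIST v1.1 and by irRC, will be estimated separately in squamous and non-squamous patients as a proportion of treated patients of that subtype, with exact binomial 95% CIs. The between-subtype difference will be given with its 95% CI. These results are descriptive.*

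The chi-squared test on mixed response should be dropped. Mixed response can stay as a separate descriptive item with a stated per-site definition. That definition should use what is already recorded (target-lesion diameters, non-target status and new lesions), because Appendix 6 does not require non-target lesions to be measured.

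For PD-L1, define strongly positive as 50% or more and state that the score is recorded as a whole number, so that every value falls in one class.

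The cost is wording in section 8.1.2. Sample size and visits do not change, and no new data are needed if the mixed-response definition is kept to recorded items.

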KEYNOTE-001 also validated the PD-1 biomarker using the anti-PD-1 antibody clone 22C3 (Merck) and immunohistochemistry. Tumour slides were stained and scored for neoplastic membranous staining (i.e. the TPS) as <1%, 1-49%, or >50%. Using receiver operator characteristic curve analysis they found that a PD-L1 score of >50% (strong) was the best predictor of efficacy of pembrolizumab, with a response rate of 45.2% (95%CI: 33.5 – 57.3) and a median PFS of 6.3 months. The media OS has not yet been reached. The response rates in patients who scored PD-L1 1-49% was 16.5% (95%CI: 9.9 – 25.1) and in those who scored PD-L1 <1% was 10.7% (95%CI: 2.3 – 28.2). As responses were seen across all PD-L1 scores, this clinical trial will explore the combination of pembrolizumab and lung SBRT unenriched for PD-L1 strong (57).

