#### 3.2 Treatment Regimen

The study will be conducted in two parts; an initial lung SBRT dose escalation phase (Part A), followed by a lung SBRT dose expansion cohort (Part B). The dose escalation phase is based on a 3+3 design such that patients will be treated in cohorts of 3-6 patients. A maximum of 12 patients will be allocated to one of two doses of lung SBRT in combination with pembrolizumab to determine the MTD, DLTs and RP2D. If there is more than one DLT in cohort 1, this treatment combination will be deemed as being unacceptable, and it would lead to termination of the study. Note, there is no de-escalation in cohort 1. During the dose expansion cohort, 12 patients will have lung SBRT dosed at the RP2D determined during the dose escalation phase in combination with pembrolizumab to obtain additional safety and response data. Maintenance pembrolizumab will continue until disease progression, unacceptable toxicities, the patient withdraws consent to the trial, or the patient has completed 24 months of treatment. A maximum of 24 patients will be treated in the study.

All patients will receive pembrolizumab on cycle (C) 1 day (D) 1, in Part A and B of the study. All patients will receive lung SBRT on C1D15, C1D17, and C1D19 as per lung SBRT protocol (See Appendix 3). Although C1D1 can occur +/- 3 days, C1D15, C1D17, and C1D19, must be scheduled for a Monday, Wednesday and Friday, respectively. Patients in part A will receive lung SBRT dosed at 30 Gy in 3# in cohort 1, or 54 Gy in 3# in cohort 2. Patients in Part B will receive the RP2D of lung SBRT, determined in Part A. All patients in Part A and Part B will receive pembrolizumab dosed at 200 mg every 3 weeks, until disease progression, unacceptable toxicities, the patient withdraws consent from the trial, or the patient has completed 24 months of treatment.

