## **8.2 Sample Size**

During the dose escalation phase a standard 3+3 design will be used to recruit patients into two lung SBRT dose cohorts, firstly dose level 1 and then dose level 2, and both given the same pembrolizumab fixed dose level. Each cohort will require a minimum of 3 and a maximum of 6 patients. This means that there will be a minimum of 6 and maximum of 12 patients required for dose escalation. There will then be an additional 12 patients in the expansion phase. This number has been arbitrarily chosen to get a better appreciation for the toxicity profile of the dose/treatment that maybe taken forward in a phase II study.

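### The PD-L1/response test in Section 8.1.2 ignores the order of the three expression classes; a 1-df trend test on the same classes would gain about 4 to 9 points of power, from a low base

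*Combined protocol and SAP*

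**What the plan says.** Section 8.1.2 defines the marker on a 0 to 100% scale ("PD-L1 staining is referred to as tumour proportionate score, reported as a percentage") and then cuts it into three classes: "It is classed as weakly positive (1 – 49%); strongly positive if >50%; and negative if <1" per cent. The association with response is "tested using a Chi Squared test for proportions on expression level between responders and non-responders". The test is not described as ordered, and no trend test, rank test or model on TPS itself appears elsewhere in the plan.

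The endpoint in Section 2.2.2 reads "To assess the frequency of PD-1/PD-L1 expression distribution in responders and non-responders". The objective in Section 2.1.2 is to look at response rates in relation to expression. Neither gives a direction.

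For this analysis both parts are pooled: "All patients from Part A and Part B will be used to analyse secondary endpoints". Section 3.2 caps the number ("A maximum of 24 patients will be treated in the study"), and Section 8.2 gives a "minimum of 6 and maximum of 12 patients required for dose escalation", followed by 12 in expansion. No significance level or power is stated for the PD-L1 test.

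**The concern.** Negative, weak and strong form an ordered scale, but a Pearson chi-squared test treats them as three names. It spreads its sensitivity over every possible pattern of differences, including patterns in which the middle class responds best or worst.

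The data cited in Section 1.1.4.2 follow a rising pattern: 10.7% response below 1%, then "The response rates in patients who scored PD-L1 1-49% was 16.5% (95%CI: 9.9 – 25.1"), then 45.2% in the top class. If this trial shows a similar gradient, a test that uses the order is more likely to detect it from the same table. With at most 24 patients and about six expected responders, there is little information to spare. What is at stake is a somewhat higher chance of reporting no association when a rising one exists.

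**Working it through.** **Inputs.**
- N = 24 (Section 3.2), or 6 + 12 = 18 (Section 8.2).
- Response rates 10.7%, 16.5% and 45.2% (Section 1.1.4.2).
- Two-sided 5%: an assumption.
- PD-L1 mix: an assumption. The three quoted intervals are reproduced by the Clopper-Pearson formula as 3/28 (2.3 to 28.2), 17/103 (9.9 to 25.1) and 33/73 (33.5 to 57.3), which gives 28:103:73. Section 1.1.2 puts abnormal PD-L1 expression in this cancer nearer one half, so I also took 50% negative with the positives split 103:73.
- Expected responders for 28:103:73: (28×10.7 + 103×16.5 + 73×45.2)/204 = 26.0%, and 24 × 0.260 = 6.2.

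The plan states no power for this test, so there is no figure of its own to reproduce.

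**Statistics.** Class i has n_i patients and x_i responders; p = Σx_i/N; scores s = 0, 1, 2.
- Planned: X² = Σ(x_i − n_i p)² / [n_i p(1−p)], against 5.99 (2 df).
- Trend: T = Σs_i(x_i − n_i p), V = p(1−p)[Σn_i s_i² − (Σn_i s_i)²/N], and T²/V against 3.84 (1 df).

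**One table by hand.** Rounding the expected counts for 28:103:73 gives n = 3, 12, 9 and x = 0, 2, 4, so p = 0.25 and p(1−p) = 0.1875.
- X² = 0.5625/0.5625 + 1/2.25 + 3.0625/1.6875 = 1.00 + 0.44 + 1.81 = 3.26; on 2 df, p-value 0.20.
- T = 1×(2−3) + 2×(4−2.25) = 2.5; V = 0.1875×(48 − 900/24) = 1.97; T²/V = 3.17; on 1 df, p-value 0.075.

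Nearly all of the statistic is trend, but the planned test refers it to 2 df. Exchange the weak and strong labels and X² is still 3.26, while T²/V falls to (−0.25)²/2.18 = 0.03.

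**Power.** I summed over every class allocation (multinomial) and every responder count (binomial), at two-sided 5%:

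| N, PD-L1 mix | Planned 2 df | Trend 1 df | Gain (points) | Exact unordered | Exact trend | Gain, exact (points) |
|---|---|---|---|---|---|---|
| 24, 28:103:73 | 24.1% | 33.3% | 9.2 | 21.2% | 24.0% | 2.8 |
| 24, equal thirds | 28.9% | 37.7% | 8.8 | 25.9% | 28.9% | 3.0 |
| 24, 50/25/25 | 32.7% | 38.8% | 6.1 | 28.8% | 30.7% | 1.9 |
| 24, half negative, rest 103:73 | 31.5% | 35.5% | 4.0 | 27.0% | 27.5% | 0.5 |
| 18, 28:103:73 | 16.6% | 24.9% | 8.3 | 15.1% | 16.3% | 1.2 |

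If the degrees of freedom drop when a class is empty, the planned test has 24.6% at N = 24 and 17.7% at N = 18 for 28:103:73, and the gains are 8.7 and 7.2 points.

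**Type I error**, N = 24, 28:103:73, common rate 26%: planned 4.6%, trend 5.3%, exact unordered 3.7%, exact trend 2.8%. A small part of the gain is therefore a difference in size.

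**Using TPS itself** (simulation, N = 24, TPS uniform within class). With response flat within classes, a Wilcoxon test has about 25 to 27% power for 28:103:73 against 24% for the planned test. With half negative it has about 29 to 31% against 31%. If log-odds rise linearly with TPS, it has 36.9% against 22.0%.

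**The case against.** The strongest case against is that the gain is fragile and that nothing depends on it. At least one expected cell is below 5 in 99.8% of tables at N = 24, so a cautious analyst would want exact tests. The exact trend test then has 24.0% power for the 28:103:73 mix, no better than the planned test. With half the patients negative it has 27.5%, which is below the planned 31.5%. Section 8.2 describes the expansion size as arbitrary and aimed at toxicity, and no decision rests on this test. In the main scenario even the trend test misses the association about two times in three. All of this stands, and it sets the severity.

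It does not remove the point. The asymptotic trend test keeps its type I error near 5% in the mixes enumerated. Within each type of test, asymptotic or exact, the ordered version had at least as much power in every scenario tried.

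Three stronger readings are tempting, and the documents do not support them:
- *That the protocol expects a rising relation here.* It cites one as background, from pembrolizumab without radiotherapy, and adds that responses occurred at all PD-L1 levels. It states no ordered hypothesis for this trial.
- *That cutting TPS into classes is what costs the power.* The 4 to 9 points come from ordering the same three classes. Raw TPS gains clearly only if response rises within classes, and no section says that it does.
- *That the classes are a mistake.* They are the ones scored in the cited study, whose ROC analysis picked out the top class, and they allow direct comparison with its rates.

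**Conclusion.** The point holds as a minor inefficiency. The planned test ignores the class order. If response rises with expression as in the cited data, a 1-df trend test on the same classes gains about 4 to 9 points of power at N = 24. This rests on two-sided 5%, the cited response rates, scores 0, 1, 2 and an assumed PD-L1 mix; the mix accounts for most of the range. With exact tests the gain is about 0.5 to 3 points. A reader might take 9 points as a fixed loss built into the plan, but it is the top of a range under one assumed mix. Power stays between roughly a quarter and two fifths with either asymptotic test at N = 24, so a non-significant result would say little in any case. Severity is low.

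**What to change.** In Section 8.1.2, keep the table of response rates by PD-L1 class, with exact 95% confidence intervals, as the main description. Replace the unordered chi-squared test with a two-sided 1-df test for trend (Cochran-Armitage, or linear-by-linear) on the three classes, labelled exploratory. Fix the scores at 0, 1, 2 in advance, since the choice matters: scores at the TPS midpoints give 37.3% in the main scenario. State whether the asymptotic or exact p-value will be used. Also assign a TPS of exactly 50% to a class, which the present wording does not do.

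A permutation Wilcoxon test of TPS between responders and non-responders, with the area under the ROC curve and its 95% confidence interval, may be added as support.

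The cost is a sentence or two, with no new data, assay or patients. The notes to Table 3 say that PD-L1 testing is batched until all patients are on study, so the change can be prespecified before those results exist. The one downside is less sensitivity to a non-monotone pattern, such as response highest in the weak class; the retained table would still show it.
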